### 8.4 Packaging and Labeling Information

Clinical supplies will be affixed with a clinical label in accordance with regulatory requirements.

### 8.5 Clinical Supplies Disclosure

This trial is open-label; therefore, the subject, the trial site personnel, the Overall PI and/or designee are not blinded to treatment. Drug identity (name, strength) is included in the label text; random code/disclosure envelopes or lists are not provided.

### 8.6 Storage, Handling and Preparation Requirements

As specified in the Pharmacy Manual for pembrolizumab as provided by the Merck.

Clinical supplies must be stored in a secure, limited-access location under the storage conditions specified on the label.

Receipt and dispensing of trial medication must be recorded by an authorized person at the trial site.

Clinical supplies may not be used for any purpose other than that stated in the protocol.

### **8.7 Administration**

Pembrolizumab will be administered as a 30 minute IV infusion using an infusion pump (treatment cycle intervals may be increased due to toxicity as described in Section 6). Sites should make every effort to target infusion timing to be as close to 30 minutes as possible. However, given the variability of infusion pumps from site to site, a window of -5 minutes and +10 minutes is permitted (i.e., infusion time is 30 minutes: -5 min/+10 min). Attach the infusion line to the pump and prime the line, either with normal saline (at least 25 mL) or with infusion solution as per local SOP, before starting the infusion. Maximum infusion rate should not exceed 6.7 ml/min through a peripheral or indwelling catheter. Use 30 mL normal saline to flush the infusion line at the end of the infusion if institutional guidelines allow. For more details, please see pharmacology manual.

Unused infusion solution should not be used for another infusion of the same participant or different participant.

DO NOT administer the product as an intravenous push or bolus.

DO NOT combine, dilute or administer it as an infusion with other medicinal products.

A central line is not required for Pembrolizumab administration, but may be used if available.

The following infusion set materials are compatible with Pembrolizumab

- PVC infusion set that is plasticized using Di-2-ethylhexyl Terephthalate DEHP
- PVC and tri-(2-ethylhexyl) trimellitate (TOTM) infusion set
- Polyethylene lined PVC infusion set
- Polyurethane
- Polybutadiene A sterile, non-pyrogenic, low-protein binding 0.2 to 5 µm in-line filter made of polyethersulfone (PES) or polysulfone must be used during administration to remove any adventitious particles. If the infusion set does not contain a 0.2 to 5 µm in-line filter, it is recommended to use a 0.2 to 5 µm add-on filter which may contain an extension line (the materials of the extension line and filter should be as mentioned above).

A sterile, non-pyrogenic, low-protein binding 0.2 to 5 µm in-line filter made of polyethersulfone

(PES) or polysulfone must be used during administration to remove any adventitious particles. If the infusion set does not contain a 0.2 to 5 µm in-line filter, it is recommended to use a 0.2 to 5 µm add-on filter which may contain an extension line (the materials of the extension line and filter should be as mentioned above).

### **8.8 Ordering**

Participating Institutions will order their own investigational agent (Pembrolizumab) directly from Merck using the Drug Supply Request Form. Please allow for 3 weeks for drug to arrive after the order is submitted. The Participating Institution will ensure that the pharmacy will be able to receive and store the agent according to state and federal guidelines. The local IRB should be kept informed of who will supply the agent (i.e., Merck pharmaceuticals Inc.) so that any regulatory responsibilities can be met in a timely fashion.

### **8.9 Accountability**

The investigator is responsible for keeping accurate records of the clinical supplies received from Merck or designee, the amount dispensed to and returned by the subjects and the amount remaining at the conclusion of the trial.

### **8.10 Destruction and Return**

Upon completion or termination of the study, all unused and/or partially used investigational product will be destroyed at the site per institutional policy. It is the Investigator's responsibility to arrange for disposal of all empty containers, provided that procedures for proper disposal have been established according to applicable federal, state, local and institutional guidelines and procedures, and provided that appropriate records of disposal are kept.

## **9. BIOMARKER, CORRELATIVE, AND SPECIAL STUDIES**

### **9.1 Exploratory Laboratory Correlative Studies**

As outlined above in section 2.4, we will characterize pre-treatment samples and any post-treatment samples that are resected and available using whole exome sequencing (WES), RNA-sequencing, immunohistochemistry for immune cell markers and in situ hybridization for PD-1 and PD-L1 mRNA.

### **9.2 Background**

Comprehensive genomic characterization of samples collected as part of our proposed clinical trial will allow us to identify biomarkers of response and provide insight into mechanisms of resistance to immunotherapy. Pre-treatment formalin fixed paraffin embedded (FFPE) tissue samples will be collected within 30 days after enrollment and post-treatment FFPE samples will be collected in patients that progress on treatment if surgery is clinically warranted and if the sample tissue is available. Analytic tools for WES have been developed for our prior studies and will be used to elucidate the genomic evolutionary profiles in matched tumor samples. As previously described in our work showing that meningioma cells express PD-L1, we will characterize PD-L1 expression, tumor infiltrating lymphocytes and PD-1 expressing lymphocytes.

### **9.3 Methodology**

#### **9.3.1 RNAscope assay and evaluation**

FFPE sections will be hybridized separately with Probe-Hs-PDL1-v2 and a PD-1 specific probe and then visualized. Probe-DapB and Probe-Hs-PPIB will be used as negative and positive controls respectively. Stained slides will be digitally scanned, then visually evaluated by two pathologists. We will use an open-source CellProfiler image analysis software (<http://www.cellprofiler.org/>) to analyze the number of dots per cell using a customized analysis pipeline that we have developed, optimized and tested. ([http://www.cellprofiler.org/published\\_pipelines.shtml](http://www.cellprofiler.org/published_pipelines.shtml)).

#### **9.3.2 Immunohistochemistry and evaluation**

The following primary antibodies will be used to characterize the tissue pre and post-treatment FFPE tissue sections from this study: LCA (1:600 dilution, Cat# M0701; Dako, CA), CD3 (1:250 dilution, Cat# A0452; Dako, CA), CD4 (1:80 dilution, Cat# M7310; Dako, CA), CD8 (1:100 dilution, Cat# M7103; Dako, CA), CD20 (Ready to Use, Cat# N1502 RTU; Dako, CA), FOXP3 (1:50 dilution, Cat# 320102; Biolegend, CA), PD-1 (1:300 dilution, Cat# 315M-95; Cell Marque, CA), PD-L1 (1:36 dilution, Cat# 10084-R015; Sinobiological, China), PD-L1 (1:125 dilution, Cat# 405.9A11; courtesy of [name] lab DFCI). We will use an Aperio scanner to acquire digital images from all stained slides. Digital images will be scored using Aperio ImageScope software.

Furthermore, PD-L1 expression will be measured from any remaining archival tissue and correlated with response. PD-L1 expression will be measured by the QualTek assay as well as with RNA-Seq as specified below in 9.3.3.

### **9.3.3 RNA-sequencing**

RNA Sequencing from FFPE includes plating, poly-A selection and cDNA synthesis, library preparation, sequencing, sample identification QC, and data storage. RNA will be extracted from tissue sections and RNA libraries will be prepared for sequencing by NEBNext Ultra RNA Library Prep Kit for Illumina (New England BioLabs, Ipswich, MA), including the removal of large and small RNA, synthesis of cDNA, and construction of cDNA libraries. Libraries will be barcoded using NEBNext Multiplex Oligos for Illumina (NEB). Libraries will be sequenced using Illumina HiSeq 2500, with paired-end 100bp reads. We will follow the analytic pipelines as previously described. Paired-end reads will be aligned to UCSC human transcriptome 19 (hg19) using TopHat (Bowtie v2.0.9). Alignment quality and read distribute will be assessed via SAMtools (v0.1.19). Transcript assembly will be conducted using cufflinks (v2.2.1). Normalized expression data will be generated from aligned BAM files using cuffnorm and cuffdiff. Statistically significant genes differentially expressed between responder samples and non-responders will be determined.

### **9.3.4 Whole exome sequencing**

Whole-exome sequencing will be performed on DNA isolated from unstained FFPE tissue sections and matched DNA from blood. Sequencing will be performed to a mean depth of 100X, and analysis proceeded as previously described. Raw sequencing data will be processed using the Picard tools pipeline and the Genome Analysis Toolkit (GATK). Mutation analysis for single nucleotide variants (SNV) will be performed using MuTect v1.1.4, indel calling performed using the GATK SomaticIndelDetector tool; SNVs and indels annotated using Oncotator. To analyze somatic copy number alterations from whole exome data, we use the ReCapSeg algorithm, which assesses homologue-specific copy ratios (HSCRs) from segmental estimates of multipoint allelic copy-ratios at heterozygous loci incorporating the statistical phasing software (BEAGLE) and population haplotype panels (HAPMAP3). Phylogenetic analysis will be performed as previously described. Targeted sequencing of panels of genes will be performed in a select subset of cases as previously described.

### **9.3.5 MRI Studies**

All MRIs including baseline and any follow-up time points during the study duration should be sent to [name]. These studies can be batched but should be sent at least every 3 months. The MRI can be sent in the mail via CD/DVD to [name] at the address below or electronically transferred via Partners Secure File Transfer at: <https://transfer.partners.org/courier/web/1000@/wmLogin.html>

For CD/DVD shipping, please label DVD with patient ID and time point. Send to:

[name]

[name]  
[name]  
[name]

### **9.3.5.3 Statistical Considerations**

Exploratory analyses will be conducted. As data permit, analyses of the MRI parameters will be summarized by descriptive statistics, including mean, median and standard deviation. Differences in these parameters between responders and non-responders will be compared with parametric or nonparametric techniques as permitted by the data. For correlative analyses, Cox proportional hazards model will be used to explore the relationship between parameters measured at baseline and PFS and OS. Logistic regression will be used to explore the relationship between parameters measured at baseline and the binary outcome of alive and progression-free at 6 months (APF6).

Overall, the plan is to determine whether the baseline measurements are prognostic for the entire group. We will determine whether there is an association between the baseline measurements and response adjusting for the patient cohort. A priori we do not think that the association between the baseline measurements and response will depend on the type of mutation and treatment. However, if the association between baseline measurements and response are not found to be statistically significantly associated, we will do subgroup analyses to determine if there might be differences in the association between baseline variables and response among the groups. Specifically, we will do perform the analysis for each group separately. We will also do tests for interaction between the cohort group and the baseline variable, though these will likely not have sufficient power due to the small sample sizes.

The overall plan for determining whether a change in the parameters from baseline is associated with response is to first evaluate the association with the change between baseline and first MRI time point (6 weeks into therapy). An additional analysis will be done that uses all the available MRI assessment time points. To account for multiple MRI time points, we will treat the change in MRI from baseline as a time-dependent variable (which could change at each assessment).

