checkpoint blockade with pembrolizumab. We are thus proposing a prospective Phase 2 study of the PD-1 inhibitor pembrolizumab in patients with recurrent high grade (WHO grade II and III) using a dose schedule that has demonstrated efficacy in systemic tumors. We propose to investigate the activity of pembrolizumab in a single cohort. We propose to incorporate monitoring with MR imaging, and pathology correlates from tissue resections (IHC markers for characterizing the immune infiltrate including PD-1 expressing cells and PD-L1 expression of the tumors via IHC and mRNA in situ hybridization/quantitative RNAscope), and next generation DNA sequencing and RNA-sequencing to identify genetic and imaging predictors of response.

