## 5. TREATMENT PLAN

### 5.1 Treatment Regimen

Pembrolizumab will be administered every 3 weeks, with 21 consecutive days defined as a treatment cycle. Treatment will be administered on an outpatient basis. Reported adverse events and potential risks are described in Section 7. Appropriate dose modifications are described in Section 6. No investigational or commercial agents or therapies other than those described below may be administered with the intent to treat the participant's malignancy.

The treatment to be used in this trial is outlined below in the table below.

Table 2: Dose of Pembrolizumab

Drug	Dose/Potency	Dose Frequency	Route of Administration	Regimen/Treatment Period	Cycle Length
Pembrolizumab	200 mg	Q3W	IV infusion	Day 1 of each 3 week cycle	3 weeks

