## **13.0 STATISTICAL CONSIDERATIONS**

### **13.1 Study Design**

There will be a single phase 2 arm in this study. Patients with recurrent or residual meningioma will be eligible for this trial. There is no planned interim analysis.

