### **13.4 Stratification Factors**

NA

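### The baseline-MRI analysis adjusts for, splits by and tests interaction with a cohort that this single-cohort trial does not have, and opens subgroup testing only after a negative overall result

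*Combined protocol and SAP*

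**What the plan says.** The second paragraph of section 9.3.5.3 deals with baseline MRI measurements. Its aim is to learn whether they are prognostic in the whole group, and it then states: "We will determine whether there is an association between the baseline measurements and response adjusting for the patient cohort". It adds: "A priori we do not think that the association between the baseline measurements and response will depend on the type of mutation and treatment". The fallback follows: "if the association between baseline measurements and response are not found to be statistically significantly associated, we will do subgroup analyses", and "Specifically, we will do perform the analysis for each group separately". A test of interaction between cohort group and baseline variable is also planned, with an admission that power will probably be too low. No significance level or multiplicity rule is given.

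The design sections describe a simpler trial:

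- Section 2.3: "We propose to investigate the activity of pembrolizumab in a single cohort".
- Section 13.1: "There will be a single phase 2 arm in this study".
- Section 5.1: one drug on one schedule, "Pembrolizumab will be administered every 3 weeks, with 21 consecutive days defined as a treatment cycle".
- Section 13.4, on stratification factors, is marked not applicable.

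Section 13.8 also covers imaging biomarkers. It relies on descriptive statistics and simple comparisons of response groups, and mentions neither a cohort nor a triggered subgroup step.

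**The concern.** The paragraph reads as if it belonged to a trial with several cohorts. Nothing in the documents says what cohort, group or cohort group means here, and the eligibility criteria in section 3 set up no mutation-defined groups. An analyst who reaches this step must either drop it or invent groups once data are in hand. Candidates will be available: mutation type from the sequencing in section 9.3.4, or WHO grade, since grades II and III are the target (section 1.2) and grade I is also admitted (section 3.1.3).

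The trigger makes that choice matter more. Further tests open only when the main test fails, so a null result gains extra chances to become a positive one. At stake is the credibility of any reported link between baseline MRI and response. No treatment decision depends on it.

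**Working it through.** **The plan's own figure.** Section 9.3.5.3 states no operating characteristic. The only design figure is the primary rule in section 13.6: at least 10 of 24 patients, 26% versus 52%, one-sided 0.1. With X binomial(24, p), P(X ≥ 10 | 0.26) = 0.069 and P(X ≥ 10 | 0.52) = 0.888. This agrees with the stated level of 0.1 and power of at least 88%. The MRI point does not bear on it.

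**Step 1: can the terms be estimated?** For 24 patients in one cohort, the cohort column is constant.

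- Intercept + baseline MRI + cohort: 3 columns, rank 2.
- Adding cohort × baseline: 4 columns, rank still 2.

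The cohort and interaction coefficients do not exist. The baseline coefficient does, and equals the unadjusted one. Analysing each group separately repeats the overall analysis.

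**Step 2: what does the trigger do?** The sequence is an overall test at level a, then, if not significant, one test per group. It was simulated with no true association.

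Inputs from the documents: 24 evaluable patients (section 13.3), and responder shares of 26% and 52%, borrowed from the progression-free rates in section 13.6. Assumptions, because the documents are silent: two-sided a = 0.05, the number and size of groups, and responder shares of 10% and 40%. The 10% setting is there because response might mean objective response, which section 2.1 puts at 0% in nearly all earlier studies.

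Exact rank-sum tests, 20,000 simulated trials per cell, chance of at least one false positive per MRI parameter (simulation error about 0.2 points):

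| Group sizes | 10% responders | 26% | 40% | 52% |
|---|---|---|---|---|
| 24 (one cohort) | 3.1% | 4.5% | 4.7% | 4.5% |
| 12 / 12 | 4.5% | 9.5% | 10.4% | 11.0% |
| 14 / 10 | 5.0% | 9.1% | 9.8% | 9.6% |
| 20 / 4 | 4.0% | 6.0% | 6.4% | 6.7% |
| 8 / 8 / 8 | 3.3% | 7.1% | 9.7% | 10.1% |
| 14 / 8 / 2 | 4.0% | 7.5% | 9.1% | 8.9% |

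The overall test alone ran at about 3–5% in every row. In the one-cohort row the fallback changes nothing.

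**Step 3: a different test.** Correlation tests on two continuous variables, equal groups, 20,000 simulated trials:

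| Level | Groups | Overall only | + group tests | + interaction test |
|---|---|---|---|---|
| 0.05 | 2 | 5.0% | 11.6% | 13.5% |
| 0.05 | 3 | 4.9% | 16.6% | 17.8% |
| 0.10 | 2 | 10.3% | 22.5% | 24.9% |
| 0.10 | 3 | 10.0% | 30.9% | 32.2% |

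As a rough check, three independent tests at 0.05 give 1 − 0.95³ = 14.3%. The two-group figure of 11.6% lies below this because the overall and group tests overlap. Rank-sum figures are lower because exact tests in small, unbalanced samples are conservative.

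All these rates are per MRI parameter, and the number of parameters is not stated.

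**The case against.** The best defence is that this is leftover wording in a section that is labelled exploratory, is to be done as data permit, and concedes low power for interactions. With one cohort the adjusted model simply becomes the unadjusted one, and the fallback repeats the same test. That stands, and it limits the point.

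Four stronger readings are tempting, and the documents do not support them.

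- A reader might infer that the model adjusts for mutation type and treatment as well. It adjusts for cohort only. The other two appear in a sentence saying that the association is not expected to depend on them.
- A reader might infer that exploratory objective 2 (section 1.4) is left without a usable analysis. That objective concerns changes in MRI parameters. The third paragraph of section 9.3.5.3 covers changes, with no cohort term, groups or trigger. For baseline values, the descriptive summaries, responder comparisons, Cox models and logistic regression can also run.
- A reader might infer that the text as it stands inflates false positives. With one literal cohort the inflation is zero. It arises only if groups are supplied later.
- A reader might infer that WHO-grade adjustment is required. At 26–52% of 24, only about 6 to 12 patients would be progression-free at 6 months (0.26 × 24 = 6.2; 0.52 × 24 = 12.5). A three-level grade term could be too sparse to fit stably.

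What the defence does not answer is that the groups are undefined and a negative result is the stated reason to look for some.

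**Conclusion.** The point holds as a narrow one. In the baseline-MRI paragraph, the cohort and interaction terms cannot be estimated and the per-group analyses refer to nothing defined in the trial. This follows from the documents alone.

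The multiplicity problem is conditional. If two or three groups are supplied after a negative overall test, the rank-sum false-positive chance per parameter goes from about 3–5% to about 4–11%, except with three equal groups and 10% responders, where it barely moves (about 3%). Correlation tests at 0.05 give about 12–17%, or 13–18% with the interaction test. No single figure should be quoted, because the level, the groups and the responder share are all assumptions.

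The change-from-baseline analysis, the other exploratory MRI analyses and the primary conclusion are not affected. This is a low-priority correction.

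**What to change.** In section 9.3.5.3, delete the cohort adjustment, the sentence on mutation type and treatment, the per-group repeat, the interaction test and the rule that makes subgroup analysis depend on a non-significant result. Keep the unadjusted whole-group analysis of each baseline parameter.

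If a subgroup is wanted, WHO grade being one possibility, name it before the MRI data are analysed. Report its estimates descriptively whatever the overall result, and label them hypothesis-generating. Align the wording with section 13.8.

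The cost is a text change with no new data or procedures. What is lost is a subgroup search that the plan already expects to be underpowered.

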### 1.4 Exploratory Objectives

1. To determine molecular biomarkers of response using RNAscope in situ hybridization methodologies for immune checkpoint markers, immunohistochemistry to characterize the immune infiltrate and next generation DNA and RNA sequencing.
2. To determine if changes in brain MRI parameters correlate with tumor response.

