### 11.3.1.2 Evaluation of Best Overall Response

The best overall response is the best response recorded from the start of the treatment until disease progression/recurrence (taking as reference for progressive disease the smallest measurements recorded since the treatment started). The patient's best response assignment will depend on the achievement of both measurement and confirmation criteria. If a response recorded at one scheduled MRI does not persist at the next regular scheduled MRI, the response will still be recorded based on the prior scan, but will be designated as a non-sustained response. If the response is sustained, i.e. still present on the subsequent MRI at least four weeks later, it will be recorded as a sustained response, lasting until the time of tumor progression. Participants without

measurable disease may only achieve SD or PD as their best “response.”

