#### 11.4.6 Progression-Free Survival

Overall Survival: Overall Survival (OS) is defined as the time from randomization (or registration) to death due to any cause, or censored at date last known alive.

Progression-Free Survival: Progression-Free Survival (PFS) is defined as the time from randomization (or registration) to the earlier of progression or death due to any cause. Participants alive without disease progression are censored at date of last disease evaluation.

Time to Progression: Time to Progression (TTP) is defined as the time from randomization (or registration) to progression, or censored at date of last disease evaluation for those without progression reported.

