### **13.2 Endpoints**

#### **Primary Endpoints:**

The primary endpoint is progression-free survival at 6 months (PFS6). PFS6 is defined as not having progressive disease or death within six months of the first day of treatment. Contrast-enhanced cranial magnetic resonance imaging (MRI) will be performed every 6 weeks. Standard response criteria will be used (see [Section 11.0](#)).

All patients meeting the eligibility criteria that have signed the consent form and have begun treatment will be considered evaluable for the analysis of primary endpoint.

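### The week-6 MRI change is tested against a response that the week-6 scan itself helps to score, so for size-related parameters part of any association is built in

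*Combined protocol and SAP*

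**What the plan says.** Exploratory objective 2 (Section 1.4) is "To determine if changes in brain MRI parameters correlate with tumor response". Section 9.3.5.3 opens its plan for this with "The overall plan for determining whether a change in the parameters from baseline is associated with response", and the first step is to "first evaluate the association with the change between baseline and first MRI time point (6 weeks into therapy". A further analysis uses all MRI time points and treats the change as a time-dependent variable. In the same section, PFS, OS and 6-month progression-free status are linked to parameters measured at baseline, not to change.

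The outcomes are counted from before the week-6 scan. Section 11.3.1.2 states: "The best overall response is the best response recorded from the start of the treatment until disease progression/recurrence". If a response seen at one scan is gone at the next, "the response will still be recorded based on the prior scan, but will be designated as a non-sustained response". Section 13.2 states: "PFS6 is defined as not having progressive disease or death within six months of the first day of treatment". Section 11.4.6 counts PFS from registration.

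Section 13.2 also states: "Contrast-enhanced cranial magnetic resonance imaging (MRI) will be performed every 6 weeks". Section 9.3.5 collects these study MRIs for the imaging work and describes no separate research scan. Section 11.3.3 judges radiographic progression on enhancing tumour only and dates confirmed progression back to the first scan that met the criteria.

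**The concern.** The week-6 MRI has two roles. It supplies the change value, and it is the first on-treatment scan on which response or progression can be recorded. If the parameter is tumour size, enhancement or something close to them, a patient whose tumour grew by week 6 can have an adverse predictor value and an adverse outcome from the same image. A patient whose tumour shrank can have the reverse. The first change analysis is not restricted to patients still event-free after that scan, and it does not count the outcome from there.

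The rationale (Section 2.3) looks for imaging predictors of response. An association that arises because one scan is on both sides is not prediction. With about 24 patients, it could be carried forward as an imaging biomarker that says nothing about what happens after week 6.

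**Working it through.** **The plan's own figure.** The documents give no figure for the MRI-change analysis. The nearest is the power in Section 13.6: at least 10 of 24, 26% against 52%, one-sided exact binomial test at 0.1. Recomputed, P(X ≥ 10 | 24, 0.52) = 0.888 and P(X ≥ 10 | 24, 0.26) = 0.069. This agrees with the stated power of at least 88%, so the two rates and n = 24 are used below.

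**Events by week 6.** Assume a constant hazard and take 6 months as 26 weeks. Then S(6 weeks) = PFS6^(6/26).

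- PFS6 26%: 0.26^(6/26) = 0.733. Events by week 6: 24 × (1 − 0.733) = 6.4, or 27% of patients. Share of all 6-month failures: 0.267/0.74 = 36%.
- PFS6 52%: 0.52^(6/26) = 0.860. Events by week 6: 24 × (1 − 0.860) = 3.4, or 14% of patients. Share of all 6-month failures: 0.140/0.48 = 29%.

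These are upper bounds on the shared-scan group. They include deaths and clinical worsening before the scan, and patients without a week-6 scan have no change value.

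**False-positive rate when early change predicts nothing later.** The simulation used 4,000 runs of 24 patients. Week-6 size change is a standard normal value. Progression at week 6 occurs above the cut-off that gives the S(6 weeks) shown. Later failure is independent of the week-6 change, with probability 1 − PFS6/S(6 weeks): 1 − 0.26/0.733 = 0.645, or 1 − 0.52/0.860 = 0.395. The MRI parameter has correlation ρ with size change. Parameter values are compared between 6-month failures and non-failures by a two-sided Wilcoxon test at 0.05, first in all patients and then only in those event-free at week 6.

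| ρ | All patients, PFS6 26%: rejection (AUC) | All patients, PFS6 52%: rejection (AUC) | Landmark rejection, 26% / 52% |
|---|---|---|---|
| 1.0 | 20.3% (0.68) | 22.3% (0.65) | 3.9% / 4.3% |
| 0.8 | 14.0% (0.64) | 15.6% (0.62) | 4.3% / 4.0% |
| 0.5 | 7.0% (0.59) | 8.7% (0.57) | 4.0% / 4.2% |
| 0.3 | 5.6% (0.55) | 5.8% (0.55) | 4.0% / 4.6% |
| 0 | 4.5% (0.50) | 4.9% (0.50) | 4.4% / 4.8% |

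The landmark AUC is 0.50 throughout. The expected landmark sample is 24 × 0.733 = 17.6 or 24 × 0.860 = 20.6. The simulation treats every week-6 event as progression seen on that scan, so the all-patient rejection rates are also at the upper end.

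**Which outcome.** The simulated outcome is 6-month failure, because the documents give rates for it and no expected response rate. It is also one reading of the plan: Section 13.8, which covers imaging biomarkers, splits patients by the primary endpoint while calling it response. The overlap exists under the other two readings as well. For CR/PR, a response can be recorded on the week-6 scan (Section 11.3.1.2). If SD also counts, as in Section 13.7, a patient with SD at week 6 is already a responder on that scan.

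**The case against.** The change paragraph names only response, while the figures above are for progression. This stands as a limit on the numbers: no false-positive rate has been computed for CR/PR. The mechanism carries over, but the size is unknown.

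The week-6 scan does not always settle the outcome alone. Section 11.3.3 lets initial radiographic progression in a patient without significant clinical decline be followed for up to three months and back-dates it only if confirmed. Section 11.3.1.1 treats an unconfirmed PR as stable disease, although Section 11.3.1.2 records it as a non-sustained response. This too stands, and it lowers the overlap.

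The bias depends on the parameter. The available text does not define the MRI parameters, and for one unrelated to week-6 tumour size there is no inflation.

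A reader might infer a second fault, guarantee-time bias, because patients who die or stop before week 6 have no change value. The documents do not support this. Everyone with a change value has reached the same scan, so no group gains event-free time over another. The lost patients are a missing-data matter, and Section 11.2 already limits response evaluability mainly to re-evaluated patients. A reader might also extend the point to the PFS and OS models, but Section 9.3.5.3 ties those to baseline values, where the overlap cannot arise.

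Finally, the planned time-dependent analysis might seem to answer the point. It is an addition to the first analysis, and it repeats the overlap if it uses the value from the scan that defines the event.

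**Conclusion.** The point holds for MRI parameters related to tumour size or enhancement. As written, the first change analysis cannot separate prediction from two readings of the same scan. The inflation ranges from none (about 5% rejection at correlation 0) through 7-9% at correlation 0.5 to 20-22% when the parameter is size change itself. This assumes a constant hazard, 6-month failure as the outcome, and all week-6 events seen on the scan. The 6.4 and 3.4 of 24 are ceilings, not counts of patients whose outcome that scan decides.

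It would go too far to infer that an association will be reported whatever the truth. Even in the worst case simulated, roughly four trials in five show none. The analysis is exploratory and drives no decision, so the primary conclusion on 6-month PFS is unaffected. This is a worthwhile small correction, not a flaw in the trial.

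**What to change.** In Section 9.3.5.3, make the first change analysis a week-6 landmark analysis:

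- Include patients alive and progression-free after the week-6 scan. The outcome is progression or death after that scan, either as progression-free status to 6 months or as PFS from the landmark. State how progression that is still unconfirmed at week 6 is classed.
- For CR/PR, compare only patients not already in CR or PR at week 6, and count later responses. Leaving week-6 responders in as non-responders would misclassify the patients with most shrinkage. A definition that includes SD gives no contrast here, because everyone event-free at the landmark already meets it.
- Report the concurrent correlation between week-6 change and week-6 response as descriptive only.
- In the time-dependent analysis, use the MRI value from the scan before the event-defining scan.

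The cost is a few sentences and about 3 to 6 fewer patients for progression outcomes, leaving about 18 to 21 of 24. The response comparison also loses any week-6 responders. Section 2.1 reports response rates of 0% in nearly all earlier studies of systemic therapy, so that comparison may have very few later responders, and the progression outcome is the more usable one. The landmark restored the nominal error rate in the simulation, where later progression is independent of week-6 change. It was not tested for CR/PR.
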